# Length of Study Participation/Study Timeline

The start-up phase of this investigation will be limited to four weeks. The initiation of advertising/ recruitment and the preparation/duplication of data collection instruments will be accomplished during this phase.

It is estimated that approximately 20 couples will be enrolled each week requiring a recruitment/ enrollment phase of 15 weeks to achieve a sample size of 300 couples. A follow-up phase of 11 weeks should allow the last enrollments to complete their participation. Couples are expected to complete their study participation within nine weeks of entering the study. Eight weeks will be dedicated to analysis and report writing after completion of subject follow-up.

# Management of Claimed Broken or Torn Condoms

Claimed broken or torn condoms will be shipped to Sagami Rubber Industries Co., Ltd. (Kanagawa-ken, Japan) in bulk shipments. Condoms will be shipped in the double sealed plastic pouches provided to study subjects, encased in a single large sealable plastic bag, and placed in heavy duty cardboard shipping boxes.

# **III. Subject Compensation**

Each partner will be reimbursed with a \$150 (\$300 per couple) via a cash card at the exit phone visit (XP) for time and transportation costs associated with completing the consent visit (SV1), their SP-M or SP-F, four follow-up exchanges (E1, E2, E3, E4), a phone exit (XP), using 15 study condoms and completing 15 condom reports. If couples do not complete the study, they will be paid according to the number of visits/exchanges they attended, the number of study condoms they used, and the number of condom reports they completed.

## IV. Institutional Review and Informed Consent Procedures

Prior to enrolling study subjects, the study will be reviewed and approved by the Institutional Review Board (IRB) in accordance with FDA regulations (21 CFR Part 50, 21 CFR Part 56 and 21 CFR Part 812). A copy of the IRB approval letter and the IRB approved consent form will be sent to the sponsor. The sponsor, Essential Access Health and IRB will approve all revisions and/or amendments to the protocol in advance in writing. If required, these will be filed with the U.S. Food and Drug Administration.

Protocol violations will be reported to the sponsor, Essential Access Health and IRB in accordance with IRB requirements.

#### Informed Consent Procedure

After phone pre-screening, subjects will be emailed a copy of the informed consent to read prior to their consent visit and will be instructed not to sign the form. At the consent visit, the purpose and requirements of the study will be explained before prospective subjects are presented with an electronic informed consent form identical to the one provided prior to the visit. Subjects will also be advised that more detailed information about sexual activity will be collected than is typical of most family planning visits. Subjects will be given an opportunity to ask questions about the study condoms and/or the content of the informed consent. Subjects will be informed that their partners must also agree to participate in the study in order for them to join. If both members of the couple agree to participate, they will each electronically sign the informed consent form using Part 11 compliant software. The consent form will also be signed by the research staff member conducting the consent visit. The consent form will include each of the basic and additional elements of informed consent described in 21 CFR Part 50. All subjects will be required to provide a signed informed consent before they are enrolled in the study and will receive a copy of their fully signed informed consent form.

# V. Study Design

This study is a masked (investigators, research staff), three-arm crossover, randomized to sequence of use study designed to evaluate the functional performance (breakage, slippage) of two test polyurethane male condoms (.024mm/58mm/190mm – SAGCS-A, .018mm/55mm/170mm – SAGCS-B) each compared to a commercial natural latex condom. (.055mm/53mm/195mm - Trojan Thintensity $^{TM}$  – SAGCS-C). All three study condoms are lubricated with a silicone lubricant. Three hundred (300) couples will be enrolled and asked to use five condoms of each of the study condom type to yield a potential sample size of 1,500 uses for each type of lubricated condom. To minimize a potential learning effect, couples will be randomly assigned to one of six possible sequences of use of the study condoms:

- SAGCS-A SAGCS-B SAGCS-C
- SAGCS-A SAGCS-C SAGCS-B
- SAGCS-B SAGCS-A SAGCS-C
- SAGCS-B SAGCS-C SAGCS-A
- SAGCS-C SAGCS-A SAGCS-B
- SAGCS-C SAGCS-B SAGCS-A

From experience with previous condom breakage/slippage studies, we estimate that at least 85% of couples will complete all 15 condom uses to obtain an actual sample size of approximately 1,275 for each condom type.

The primary effectiveness endpoint of the study is to confirm noninferiority with respect to total clinical failure rates (combined breakage and slippage) of the two test male condoms independently against the control natural rubber latex male condom. As specified in ISO 23409:2011 a noninferiority margin,  $\delta$ , of 2.5% will be used.

# VI. Statistical Analysis Plan

Sample Size Justification

The power calculations to determine the minimum number of couples and condom uses will be done using the formula given in annex A of ISO 29943-1:2017 adjusted for a one-sided confidence level of 97.5%. The formula for sample size is:

$$N = \{G(P) + 1.960\}2 \times Var(\Delta) / \{(\delta - \Delta)^2\}$$

where

$$Var(\Delta) = Pt(1-Pt) \times \{1+(Z-1) \rho\}/Z + Pc(1-Pc) \times \{1+(Z-1) \rho\}/Z - 2 \rho \times \{Pt(1-Pt) \times Pc(1-Pc)\}^{1/2}$$

and G(P) is the inverse cumulative normal probability function for the specified power P, Pt and Pe are the true (unknown) total clinical failure probabilities for the test and control natural rubber latex male condoms respectively,  $\rho$  is the level of within couple correlation for failure rate, Z is the number of condoms per type used and  $\Delta = Pt - Pc$ .

A correlation factor of 0.2 for the within couple total clinical failure rate between the test polyurethane and control natural rubber latex male condoms, and an upper limit of 4% combined failure rate, and a minimum power of 90% will be used for the sample size calculations. Assuming 85% of condom uses meet inclusion criteria (1,275 condom uses), the statistical power is estimated at 95% according to the method of calculation given in Annex A of ISO 29943-1: 2017.

# Statistical Objectives

The primary effectiveness endpoint of the study is to confirm noninferiority with respect to total clinical failure rates (combined breakage and slippage) of two test polyurethane male condoms against a control natural rubber latex male condom. Each of the two test polyurethane male condoms will be compared independently against the control natural rubber latex male condom. A non-inferiority margin, for expected test condom total failure rate — expected control natural rubber latex male condom total failure rate of 2.5% as specified in ISO 23409:2011 will be used to assess the results. This three-arm functionality study with two test polyurethane male condoms and one control natural rubber latex male condom will be conducted in accordance with ISO 29943-1:2017.

Each test polyurethane male condom will be assessed independently against the control natural rubber latex male condom. For each comparison, the study hypotheses will be:

Null Hypothesis, H0: Expected test condom total clinical failure rate – expected control natural rubber latex male condom total clinical failure rate  $\geq \delta$ , where  $\delta = 2.5\%$ ;

Alternative Hypothesis, HA: Expected test condom total clinical failure rate – expected control natural rubber latex male condom total clinical failure rate <  $\delta$ , where  $\delta$  = 2.5%;

For each of the comparisons (i.e., each of the two test condoms versus control condom), if the null hypothesis of inferiority is rejected using an appropriate test statistic, then the alternate hypothesis of non-inferiority will be accepted. Based on this set of co-primary hypotheses, either or both test condoms may be declared non-inferior to the control condom.

We will use the Bonferroni correction to adjust the power for the three-arm study. As a consequence, one-sided upper limits of the 97.5% confidence intervals rather than 95% confidence intervals specified in the FDA guidance document and ISO 23409:2011 will be used to assess whether the non-inferiority hypotheses using a non-inferiority margin of 2.5% are accepted or rejected. To meet the noninferiority requirement the upper 97.5% bound of the one-sided 97.5% confidence interval, *U*, shall be equal to or less than 2.5%, i.e.

$$U = (\hat{P}e - \hat{P}c) + 1.960 SE$$

where  $(\hat{P}e - \hat{P}c)$  is the estimated difference in total clinical failure rates between the test and control latex condoms and SE is the standard error of the difference (Taylor ).

Taylor (ibid) provides a simple formula for estimating the standard error for paired differences in observed failure rates among study couples. This method, however, requires all couples to provide data for both condom types and does not allow for within couple correlation of failure rates (clustering). To overcome these limitations the method of Generalized Estimating Equations (GEE) will be used to estimate the regression parameters and their standard errors (Diggle et al , Taylor and Dominik ).

The primary effectiveness of the condoms will be analysed by GEE separately for each of the two polyurethane test condoms against the common control natural rubber latex male condom using the PROC GEE procedure in SAS (or R if SAS is not available to the analyst) with an identify link function and an independent working correlation structure to calculate the limits of the one-sided upper 97.5% confidence intervals for the difference in the total clinical failure rates for the test polyurethane male condoms minus the control natural rubber latex male condom.

For each separate primary analysis, couples will need to have reported use of at least one test polyurethane male condom and one control natural rubber latex male condom for vaginal intercourse. Non-use of 5 condoms of each type will assumed to be non-informative for this primary analysis. We will report the amount of missing data per condom type; explore possible confounding due to differential missing data by type; and perform a sensitivity analysis based on 'completers' (i.e., use of all 5 condoms of each type being compared). For analysis purposes missing outcome data for individual condom uses will be assumed to be missing completely at random. The potential for informative cluster sizes and resulting bias (e.g. if couples with higher

<sup>1 Taylor, Issues in the design, analysis and interpretation of condom functionality studies, Contraception 80 (2009) 237 - 244

<sup>2 Diggle, Heagerty, Laing and Zeger, Analysis of longitudinal data, 2nd ed. Oxford University Press; 2002

<sup>3 Taylor and Dominik. Noninferiority testing and crossover trials with correlated binary outcomes and small event proportions with applications for the analysis of condom failure data, J Biopharm Statistics, 9 (2) 365 – 377 (1999)

failure probabilities use fewer condoms of either condom type) will be explored to the extent possible in sensitivity analyses. We will also assess the reasons for missing data by condom type in order to examine the assumption of randomness of missing data.

The power calculation used to determine the sample size is based on the assumption that 85% of condom uses will meet the inclusion criteria (1,275 condom uses). The 85% assumption is based on past experience of running studies of this nature. The use of a high initial power target of 95% for the calculations provides a significant level of protection against the consequences of higher than expected discontinuation rates with resulting loss of missing primary effectiveness data. If the completion rate drops to 75%, power will still exceed 90%. Even if the completion rate drops to a low as 60% the power to conclude noninferiority will remain marginally higher than 80%.

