Sagami Rubber Industries, the manufacturer of the condoms, has been manufacturing condoms since 1934 and polyurethane condoms since 1990. Sagami polyurethane condoms are available in most countries throughout the world and the test condoms are currently marketed in Japan and throughout Asia demonstrating years of safe use of the product.

The primary objective of this study is to evaluate the breakage, slippage and acceptability of two test polyurethane male condoms of different thicknesses and size (0.024mm/58mm/190mm – SAGCS-A and 0.018mm/55mm/170mm – SAGCS-B) compared to a control commercial natural rubber latex male condom (Trojan Thintensity $^{\text{TM}}$  – 0.055mm/53mm/195mm - SAGCS-C). Acceptability will be evaluated by comparing physical attributes of the polyurethane and latex condoms, as well as perceptions about purchasing and using the products and condoms in general. The study will be conducted in accordance with ISO 29943-1:2017.

The Statistical Analysis Plan in Section VI. includes details of the methods of analysis that will be used. The primary effectiveness endpoint of the study is to confirm noninferiority with respect to total clinical failure rates (combined breakage and slippage) of two test polyurethane male condoms against a control latex condom. Each of the two test polyurethane male condoms will be compared independently against the control latex condom. A non-inferiority margin for the difference between the test condom total failure rate – the control natural rubber latex male condom total failure rate of 2.5% as specified in ISO 23409:2011 will be used to assess the results.

Test polyurethane condom SAGCS-A will be considered non-inferior to the control latex condom if a formal test of inferiority is rejected. Separately, test polyurethane condom SAGCS-B will be considered non-inferior to the control condom if a formal test of inferiority is rejected. Hence, one or both test condoms may be declared non-inferior based on the results of this three-arm functionality study. The study will be considered successful if either one or both of the test polyurethane condoms complies with the primary effectiveness endpoint.

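### Should the two condom comparisons use a Holm step-down instead of single-step Bonferroni?

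*Combined protocol and SAP*

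**What the plan says.** There are two test condoms and one shared control, and each test condom has its own non-inferiority hypothesis with a 2.5-point margin. On multiplicity, Section VI (Statistical Objectives) says "We will use the Bonferroni correction to adjust the power for the three-arm study". The sentence after it gives the consequence: the plan uses "one-sided upper limits of the 97.5% confidence intervals rather than 95% confidence intervals specified in the FDA guidance document and ISO 23409:2011". The decision rule follows: "To meet the noninferiority requirement the upper 97.5% bound of the one-sided 97.5% confidence interval", written as difference + 1.960 SE, may not exceed 2.5%. The GEE analysis is set up to deliver the same quantity, the "limits of the one-sided upper 97.5% confidence intervals for the difference in the total clinical failure rates".

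Two further statements matter here. The condoms get separate verdicts: "Each test polyurethane male condom will be assessed independently against the control natural rubber latex male condom", and "either or both test condoms may be declared non-inferior to the control condom". The study-level criterion in the Introduction is an either/or rule: "The study will be considered successful if either one or both of the test polyurethane condoms complies with the primary effectiveness endpoint".

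The plan names no family-wise error rate and no step-down procedure, and it gives no power for both condoms passing together.

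**The concern.** Replacing a one-sided 95% bound by a 97.5% bound for two comparisons implies a family-wise error of 2 × 2.5% = 5%, one-sided. Single-step Bonferroni is not the most powerful way to hold that level. Holm's procedure starts with the same 97.5% test. Once one condom has passed, it judges the other on its one-sided 95% bound. It rejects whatever Bonferroni rejects, and sometimes more, from the same estimates and standard errors.

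Under the plan, then, a condom can fail on its 97.5% bound although its 95% bound meets the margin and the other condom has passed. Two commercial products are under test, so losing the second claim has a real cost. The quoted sentence also says that the correction adjusts power. A multiplicity correction controls type I error, so a reader may wonder whether it was understood and applied correctly.

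**Working it through.** **1. Is the rule applied consistently?** The sample-size formula (Section VI, Sample Size Justification) uses 1.960, the decision rule uses 1.960, and the GEE limits are one-sided 97.5%. All three agree.

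**2. Does it control the error?** By the Bonferroni inequality the family error is at most 0.025 + 0.025 = 0.05, whatever the correlation. With both condoms at the margin it is 1 − 0.975² = 4.94% if the two test statistics are uncorrelated, and 4.54% at correlation 0.5.

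**3. Does the stated power reproduce?** The plan gives a failure rate of 4%, a within-couple correlation ρ = 0.2, Z = 5 condoms per type, a margin of 0.025, and 300 couples with 85% completing (255 couples, 1,275 uses per type). Equal true rates (Δ = 0) are assumed here, because that reproduces the plan's figure.

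- Var = 0.04 × 0.96 × (0.36 + 0.36 − 0.40) = 0.0384 × 0.32 = 0.012288, where 0.36 = (1 + 4 × 0.2)/5.
- SE = √(0.012288/255) = 0.00694.
- Power = Φ(0.025/0.00694 − 1.960) = Φ(1.641) = 94.96%, against a stated 95%.

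The same formula gives 92.3% at 75% completion (225 couples) and 85.7% at 60% (180 couples). Both agree with the plan's statements that power stays above 90% and above 80%.

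**4. What would Holm add?** The joint calculation needs the correlation between the two contrasts. The plan gives ρ = 0.2 for test against control only; assume the same value between the two test condoms. Then the covariance is 0.0384 × (0.36 − 0.20), the variance is 0.0384 × 0.32, and the correlation is 0.16/0.32 = 0.5.

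Under Bonferroni both pass when both statistics reach 1.960. Under Holm both pass when the larger reaches 1.960 and the smaller 1.645. From the bivariate normal distribution:

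| Couples | Both pass, Bonferroni | Both pass, Holm | At least one passes, either rule |
|---|---|---|---|
| 255 | 91.2% | 95.2% | 98.8% |
| 225 | 86.8% | 92.4% | 97.8% |
| 180 | 76.8% | 85.1% | 94.6% |

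A simulation of 4 million draws at 255 couples gave 91.15%, 95.21% and 98.77%. The last column is the plan's own success criterion. It cannot change, because Holm's first step is the Bonferroni test.

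**5. Sensitivity at 255 couples.** With a contrast correlation of 0, both-pass power goes from 90.2% to 95.0%; with 0.75, from 92.2% to 95.6%. If both test condoms fail at 4% and the control at 3.5%, it goes from 74.5% to 83.5%.

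**6. What would Holm cost?**

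- Once the other condom has passed, an inferior condom's own error can rise from 2.5% to 5%.
- The largest observed difference that passes rises from 2.5 − 1.960 × 0.694 = 1.14 points to 2.5 − 1.645 × 0.694 = 1.36 points.
- A condom could be declared non-inferior with a 97.5% bound of up to 2.5 + (1.960 − 1.645) × 0.694 = 2.72%, above the margin.
- One condom's verdict would depend on the other's result, although the Introduction, Section V and the Statistical Objectives all call for separate or independent comparison.

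**The case for a change.** The best argument for changing is that Holm is valid, never less powerful, and runs on the same GEE output. The gain is largest in the low-completion scenarios the plan itself discusses. At 75% and 60% completion the plan's reassurances (above 90% and above 80%) hold for each condom but not for both together under Bonferroni (86.8% and 76.8%); under Holm they would (92.4% and 85.1%). A condom passing at Holm's second step would still meet the margin at the 95% level that the plan attributes to the FDA guidance and the ISO standard.

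The arithmetic stands, but it does not show a defect. The plan claims no joint power, so no stated figure is missed. At planned completion, both-pass power under Bonferroni is 91.2%, already above the 90% minimum that the plan sets for its sample size.

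Nor is the change free. The SAP is part of the protocol, so Section IV would require advance written approval from the sponsor, the research organisation and the IRB. Timing is delicate as well. Under Section IX, staff stay masked until the data have been analysed and tabulated. A switch made merely before unmasking could therefore follow a look at results by condom code, which would undermine the error control.

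The criticism of the wording is fair as language: the correction governs the error rate, not power. But the next sentence states the operative confidence level, and the power calculation is indeed adjusted to that level. Nobody running the analysis would be misled.

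**Conclusion.** The concern does not hold. Single-step Bonferroni at one-sided 97.5% is a valid, prespecified and consistently applied rule. It keeps the family error within the implied 5%, and it delivers the stated 95% power per comparison.

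Holm would add about 4 points to the chance that both condoms pass at 255 couples (95.22 − 91.16 = 4.06), and about 3 to 5 points for contrast correlations from 0 to 0.75. It would add nothing to study success. These figures assume equal true failure rates of 4%; the central one also assumes a within-couple correlation of 0.2 between the two test condoms, which the plan does not give. The gain is larger if completion is lower or the test condoms are somewhat worse than control.

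Against that gain stand a weaker error limit for the second condom and the loss of self-contained verdicts, which the plan asks for repeatedly. A sponsor can reasonably prefer either rule, so keeping Bonferroni is a design choice and not a flaw.

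### The primary GEE names no period term although sequences are randomised against a potential learning effect; adding period gives a small gain in precision and guards against a small bias

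*Combined protocol and SAP*

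**What the plan says.** Section V (Study Design) describes a three-period crossover in which each couple uses five condoms of each type: "To minimize a potential learning effect, couples will be randomly assigned to one of six possible sequences of use of the study condoms". Over the six sequences each type stands equally often in each period. The section does not say whether allocation is blocked or otherwise balanced, and it gives no size for the learning effect.

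Section VI, Statistical Objectives, specifies a separate GEE for each test condom against the control, "with an identify link function and an independent working correlation structure" (the link is evidently the identity link). The target is the upper limit of a one-sided 97.5% interval for the difference in total clinical failure rate, compared with 2.5%. A couple enters a comparison if it used at least one condom of each of the two types. The covariates are never written out. No period or sequence term is named there or elsewhere, so a model with condom type alone is the natural reading, though it is an inference from silence.

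The Sample Size Justification has no period component. It assumes "A correlation factor of 0.2 for the within couple total clinical failure rate" and "an upper limit of 4% combined failure rate", and for 1,275 evaluable uses per type "the statistical power is estimated at 95"%.

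**The concern.** A crossover that randomises order because of possible learning would normally carry period in its analysis model. If period is left out, any fall in failure over the 15 uses goes into the couple-level residuals: a couple that used the test condom first and the control last shows a difference that is partly learning. Randomising order averages this out of the estimate but not out of the standard error.

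Two things are at stake. The bound U may be wider than necessary in the situation the sequences were meant to handle. And if the mix of sequences among analysed couples becomes unequal in a way related to condom type, the unadjusted difference absorbs part of the period effect.

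**Working it through.** **Inputs from the plan.** One-sided 97.5% level (multiplier 1.960), margin δ = 0.025, failure rate 0.04, ρ = 0.2, Z = 5 uses per type, and 1,275 uses per type, which is 255 couples × 5. **Assumptions of this check.** No true difference (Δ = 0), and the period-specific failure rates below. The documents give neither.

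**1. The plan's own power.** With Pt = Pc = 0.04, p(1−p) = 0.0384 and {1 + 4 × 0.2}/5 = 0.36.

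Var(Δ) = 2 × 0.0384 × 0.36 − 2 × 0.2 × 0.0384 = 0.027648 − 0.015360 = 0.012288.

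SE = √(0.012288/255) = 0.00694. Power = Φ(0.025/0.00694 − 1.960) = Φ(1.641) = 95.0%. The stated 95% reproduces.

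**2. The same formula with learning.** Let the failure rates in periods 1, 2 and 3 be p1, p2, p3, with v = p(1−p). Averaging over the six sequences:

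- with period in the model: Var = 0.72 × mean(v) − 0.4 × mean of √(v_i v_j) over the three pairs of periods;
- without period: the same, plus the mean of (p_i − p_j)² over the three pairs.

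For 6/4/2%: mean(v) = 0.038133 and mean √(v_i v_j) = 0.035740, so Var with period = 0.027456 − 0.014296 = 0.013160. The added term is (0.02² + 0.04² + 0.02²)/3 = 0.000800, so Var without period = 0.013960. With 255 couples the SEs are 0.00718 and 0.00740, a ratio of 1.030. Power is Φ(1.520) = 93.6% with period and Φ(1.419) = 92.2% without.

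| Failure by period | SE ratio, without/with | Power without | Power with |
|---|---|---|---|
| 4/4/4% | 1.000 | 95.0% | 95.0% |
| 5/4/3% | 1.008 | 94.3% | 94.7% |
| 6/4/2% | 1.030 | 92.2% | 93.6% |
| 8/2/2% (extreme) | 1.081 | 87.0% | 91.5% |

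At 60% completion (180 couples) the 6/4/2% row becomes 81.0% without and 83.2% with period.

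**3. Is the unadjusted SE too large for its own estimator?** Simulation at 6/4/2%, 255 couples, 8,000 trials per setting, couple-clustered robust SE:

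- balanced sequences: mean SE 0.00837 against an empirical SD of 0.00821, about 2% too large;
- simple randomisation: mean SE 0.00836 against an empirical SD of 0.00835, so the SE is correct; the period-adjusted estimator is slightly more precise (SD 0.00821).

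Absolute power in this simulation was lower than by the formula (83.2% without and 85.1% with period under balanced allocation), because its correlation model differs. The gap of about 2 points is similar.

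**4. Dropout.** Write T for the test condom, C for the control and O for the other test condom. A couple counts once it has reached the later of its T and C periods. Suppose 15% leave after T and 5% after C or O, with failure of 6/4/2%:

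| Sequence | Retained | T minus C from period alone (points) |
|---|---|---|
| T C O | 0.8500 | +2 |
| T O C | 0.8075 | +4 |
| O T C | 0.8075 | +2 |
| O C T | 0.9025 | −2 |
| C T O | 0.9500 | −2 |
| C O T | 0.9025 | −4 |

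The weighted sum is 6.545 − 7.315 = −0.770 and the weights add to 5.22, so the expected shift is −0.770/5.22 = −0.15 points, in favour of the test condom. At 5/4/3% it is half that, −0.07. If dropout is the same after every type, each sequence has a mirror image with equal weight and the shift is exactly zero. A simulation of 300 couples with the 15% and 5% rates gave −0.14 points unadjusted and about 0 with period.

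**The case against.** The best case for leaving the model alone has four parts.

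- **Learning may be slight.** The protocol calls the effect potential and gives no size. Both partners must have used male condoms before, and both watch a demonstration video at SV1. This stands: it would be wrong to infer that the plan expects steep learning, and the larger scenarios above are illustrations only.
- **The SE is not wrong in general.** A reader might infer that the robust SE is too large whenever learning occurs. The documents do not support that. It is true only if sequence allocation is balanced, which they do not state; under simple randomisation the SE is valid and the estimator merely a little less efficient.
- **Any excess in the SE is conservative.** This stands for the SE. With a true difference of 2.5 points at 6/4/2%, simulated rejection was 2.9% (balanced) and 3.4% (simple) without period, and 3.5% with it under both. The excess over 2.5% is not caused by omitting period. The argument does not cover the shift from unequal loss, which runs towards non-inferiority.
- **Missing data are already to be examined.** A reader might infer that dropout in general biases the unadjusted difference; loss unrelated to condom type does not. The SAP also plans to report missing data by type, explore confounding from differential loss, and run a completers analysis. These are useful, but they leave the primary estimate unadjusted.

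**Conclusion.** The point holds as a modest improvement to the primary model. As written, the SAP names no period term in a design whose sequences are randomised because of possible learning. For assumed falls of 1 to 2 percentage points per period, the cost is an SE about 1% to 3% larger and about 0.3 to 1.4 power points at 255 couples. By the plan's formula, power then stays above the 90% minimum. The documents therefore do not support the inference that the omission leaves the trial underpowered; falling below 90% by that formula at 255 couples took an extreme pattern such as 8/2/2%.

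The shift towards non-inferiority is about 0.1 to 0.2 points at 6/4/2% with 15% against 5% dropout, which is small beside a margin of 2.5 points. It needs both learning and greater loss after a test condom.

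These sizes rest on Δ = 0, a mean failure rate of 4%, ρ = 0.2, and learning and dropout rates that are assumptions of this check. The direction does not depend on them: with no learning nothing is lost, and with learning the period-adjusted bound is on average the tighter one.

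**What to change.** In Section VI, Statistical Objectives, write out the primary model. Each of the two GEEs has condom type and period (1, 2, 3, categorical) as covariates, identity link, constant (normal) variance function, independence working correlation and robust standard errors clustered by couple. Base U on the period-adjusted condom coefficient, and report the model without period as a sensitivity analysis. State also in Section V whether sequence allocation is balanced.

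The cost is two extra parameters and the need to name the variance function; period follows from each couple's sequence. The variance function matters because, with period terms, fitted probabilities can approach zero under an identity link. In one simulated data set at 6/4/2% a binomial-variance fit with period gave −0.0095 (SE 0.0057), against −0.0066 (SE 0.0074) with constant variance. Without period the two fits agreed. The term should be fixed before data are seen, since adding it afterwards would be a post hoc choice.
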